7.10 Predictive and Pharmacodynamic Biomarkers

Biomarkers are objectively measured and evaluated indicators of normal biologic processes, pathogenic processes, or pharmacologic responses to a therapeutic intervention. In oncology, there is particular interest in the molecular changes underlying the oncogenic processes that may identify cancer subtypes, stage disease, assess the amount of tumor growth, or predict disease progression, metastasis, responses, or resistance to therapeutic agents. These investigations may be useful in developing markers to identify disease subtypes, guide therapy, and/or predict disease progression.

A blood sample will be collected prior to study treatment and around the time of tumor assessments to measure biomarkers (e.g., including but not limited AKT-1 and phosphorylated AKT).

In addition, any paraffin-embedded tumor samples collected independent from this study (whether before or during for the assessment of cancer) and the corresponding pathology report will be gathered by investigational sites. If paraffin blocks cannot be shipped, unstained slides and a core punch biopsy will be prepared from paraffin embedded tumor samples collected independent of the study before and during the study from each subject for analysis. These investigational studies may be useful in developing markers to identify disease subtypes, guide therapy and/or predict disease response or progression.

A tumor biopsy will be collected pre-treatment (optional Stage 2).

Refer to the laboratory manual for detailed collection and handling procedures for all predictive biomarker samples.

7.11 Sample Storage and Destruction

These blood and tumor samples and any other components from the cells may be stored for up to 20 years to research scientific questions related to cancer and/or RX-0201. The subject retains the right to have the sample material destroyed at any time by contacting the principal investigator.

The sponsor will be the exclusive owner of any data, discoveries, or derivative materials from the sample materials and is responsible for the destruction of the sample(s) at the request of the research subject through the principal investigator or at the end of the storage period. The principal investigator will provide the sponsor with the required study and subject numbers so that any remaining blood and tumor samples and any other components from the cells can be located and destroyed. If a commercial product is developed from this research project, the sponsor will own the commercial product. The subject will have no commercial rights to such product and will have no commercial rights to the data, information, discoveries, or derivative materials gained or produced from the sample. See Section 11.4 for subject confidentiality.

8. SAFETY DATA COLLECTION, RECORDING, AND REPORTING

8.1 Definitions

8.1.1 Adverse Events

An adverse event is any untoward medical occurrence in a trial subject who is administered a drug or biologic (medicinal product) or who is using a medical device; the event does not necessarily have a causal relationship with study drug administration or usage.

For this protocol, untoward medical occurrences that should be reported as adverse events include the following:

- Any unfavorable and unintended symptom, sign (including an abnormal laboratory finding), or disease temporally associated with the use of study drug, whether or not related to the study drug.
- Any pre-existing condition that increases in severity or changes in nature during or as a consequence of study drug administration.
- Any complication that occurs as a result of a protocol-mandated procedure (e.g., venipuncture, ECG, telemetry) in the study drug administration or follow-up periods.
- Any injury or accident occurring during the study drug administration, or follow-up periods. If a medical condition is known to have caused the injury or accident (e.g., a fall secondary to

dizziness), the medical condition (dizziness) and the accident (fall) should be reported as 2 separate adverse events.

- Any abnormality in physiological testing or a physical examination finding that requires clinical intervention or further investigation (beyond ordering a repeat [confirmatory] test).
- Any laboratory (e.g., clinical chemistry, hematology, urinalysis) or investigational abnormality (e.g., ECG, X-ray) independent of the underlying medical condition that requires clinical intervention, results in further investigation (beyond ordering a repeat [confirmatory] test), or leads to investigational medicinal product interruption or discontinuation unless it is associated with an already reported clinical event. If the laboratory abnormality is part of a syndrome, the syndrome or diagnosis (e.g., anemia) not the laboratory result (e.g., decreased hemoglobin) should be recorded.
- A complication related to pregnancy or termination of a pregnancy (see Section 8.7.2 for additional information).

None of the following events is considered an adverse event:

- Laboratory abnormalities not requiring clinical intervention or further investigation. Such abnormalities will be captured as part of overall laboratory monitoring.
- A diagnostic, medical or surgical procedure (e.g., surgery, endoscopy, tooth extraction, transfusion). However, the medical condition for which the procedure was performed should be reported if it meets the definition of an adverse event. For example, an acute appendicitis that begins during the adverse event reporting period should be reported as the adverse event and the resulting appendectomy should be recorded in the subject's medical records and eCRF.
- A pre-existing disease or condition or laboratory abnormality present or detected before the initial screening visit and that does not worsen.
- An intervention not associated with an untoward medical occurrence (e.g., hospitalization for elective surgery or for social and/or convenience reasons).
- An overdose without clinical sequelae.

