5.4 Subject Replacement

Subjects in Stage 1 who are enrolled but not treated and subjects who discontinue treatment before completion of Cycle 1 for reasons other than the occurrence of a DLT may be replaced. Any replacement subject will be enrolled into the same dosing group as that for the subject who withdrew.

Subjects in Stage 2 who are enrolled but not treated will be replaced.

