8.2.1 Eliciting Adverse Event Information

The investigator is to report all directly observed adverse events and all adverse events spontaneously reported by the study subject. In addition, each study subject will be questioned about adverse events at each scheduled clinic visit or during each telephone contact with the subject following initiation of study drug administration. The type of question asked should be open-ended, e.g., *“Have you had any new health problems?”* or a similar type of query.

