9.5.2 Analysis of Key Study Endpoints

9.5.2.1 Adverse Events

Each reported adverse event will be assigned a System Organ Class (SOC), a higher level group term, a high level term and a preferred term according to the current version of the Medical Dictionary for Drug Regulatory Activities (MedDRA). The severity of adverse events will be assigned in accordance with the NCI CTCAE version 4.03 guidelines.

All adverse events will be listed by subject. The subject incidence rate of adverse events occurring between informed consent and first dose of study drug will be summarized by system organ class and preferred term for the Safety Analysis Set.

The incidence rate of treatment emergent adverse events, defined as all adverse events reported as new or worsened after the start of study drug, will be summarized by treatment group, system organ class, preferred term and maximum severity (where appropriate) for all adverse events, serious adverse events, adverse events leading to discontinuation of study specified treatment, adverse events leading to discontinuation from the study and fatal adverse events using subjects in the safety population. In addition, summaries of exposure adjusted adverse event rates may also be presented. These summary tables will also be repeated for treatment related adverse events. The number and percent of subjects reporting adverse events (all, serious, and related) will be tabulated by dose levels. Narratives of all serious and fatal adverse events will also be provided.

A listing and summary of the incidence of dose limiting toxicities present will be reviewed to make dose escalation decisions in Stage 1 review (dose limiting toxicity assessment set) will also be produced by treatment group and by subject.

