### **8.10 Adverse Events**

All Adverse Events (AEs) will be listed as described on the eCRF.

An adverse event will be any untoward medical occurrence in a trial subject who is administered a drug or biologic (medicinal product) or who is using a medical device; the event does not necessarily have a causal relationship with study drug administration or usage.

For this protocol, untoward medical occurrences that should be reported as adverse events will include the following:

- Any unfavorable and unintended symptom, sign (including an abnormal laboratory finding), or disease temporally associated with the use of study drug, whether or not related to the study drug.

- Any pre-existing condition that increases in severity or changes in nature during or as a consequence of study drug administration.
- Any complication that occurs as a result of a protocol-mandated procedure (e.g., venipuncture,) in the screening, study drug administration, or follow-up periods.
- Any injury or accident occurring during the screening, study drug administration, or follow-up periods. If a medical condition is known to have caused the injury or accident (e.g., a fall secondary to dizziness), the medical condition (dizziness) and the accident (fall) should be reported as 2 separate adverse events.
- Any abnormality in physiological testing or a physical examination finding that requires clinical intervention or further investigation (beyond ordering a repeat [confirmatory] test).
- Any laboratory (e.g., clinical chemistry, hematology, urinalysis) or investigational abnormality (e.g., X-ray) independent of the underlying medical condition that requires clinical intervention, results in further investigation (beyond ordering a repeat [confirmatory] test), or leads to investigational medicinal product interruption or discontinuation unless it is associated with an already reported clinical event. If the laboratory abnormality is part of a syndrome, the syndrome or diagnosis (e.g., anemia) not the laboratory result (e.g., decreased hemoglobin) should be recorded.
- A complication related to pregnancy or termination of a pregnancy (see Section 9.7.2 for additional information).

None of the following events will be considered an adverse event:

- Laboratory abnormalities not requiring clinical intervention or further investigation. Such abnormalities will be captured as part of overall laboratory monitoring.

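### Adverse events between consent and first dose are to be tabulated but are not systematically collected, and protocol and SAP disagree on whether screening counts

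*Protocol*

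**What the plan says.** **Definition.** Protocol section 8.1.1 lists among reportable events "Any complication that occurs as a result of a protocol-mandated procedure (e.g., venipuncture, ECG, telemetry) in the study drug administration or follow-up periods" and "Any injury or accident occurring during the study drug administration, or follow-up periods". Neither item names screening. SAP section 8.10 repeats both items with a wider window; for procedure complications it reads "in the screening, study drug administration, or follow-up periods". SAP section 11 lists no changes to the protocol.

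**Elicitation.** Protocol section 8.2.1 has subjects questioned "at each scheduled clinic visit or during each telephone contact with the subject following initiation of study drug administration".

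**Schedule.** AE recording is absent from the screening list (7.2) and from the pre-dose lists for Stage 1 (7.3.1) and Stage 2 (7.5.1). The AE row is blank in the screening column of Appendices A and B and starts at Cycle 1 Day 1.

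**Procedure in the interval.** Sections 7.5.1 and 7.10 offer Stage 2 subjects an optional tumour biopsy before treatment. Footnote 4 of protocol Appendix B allows it up to 5 days before Day 1.

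**Analysis.** Protocol section 9.5.2.1 states: "The subject incidence rate of adverse events occurring between informed consent and first dose of study drug will be summarized", using the Safety Analysis Set, which section 9.2.2 restricts to subjects with at least one dose. Section 5.4 adds: "Subjects in Stage 2 who are enrolled but not treated will be replaced". The AE tables described in SAP 8.10 are treatment-emergent; none covers consent to first dose.

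**The concern.** The protocol promises a table for an interval in which it schedules no data collection. In that interval a Stage 2 subject may have a biopsy taken for research, and a non-fatal complication such as a bleed would have no scheduled point at which a site must ask about it and write it down.

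Two things would follow. First, what reaches the pre-dose table would depend on site habit. Sites that record from consent would contribute events, and sites that follow 8.1.1 and 8.2.1 to the letter mostly would not, so a low count could not be read as a low rate. Second, the subject for whom the event matters most, one who is not dosed because of it, would not be in the table at all.

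The difference between protocol and SAP adds to this. Sites work from the protocol and the analyst from the SAP, and the two documents give different windows for the same kinds of event.

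**Working it through.** The point rests on no sample size, power or error rate, so the check is a comparison of texts with two small sums.

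1. **Length of the interval.** Screening runs up to 14 days before enrolment (7.2), and dosing should follow within 5 days of enrolment (5.3): 14 + 5 = 19 days at most, nominally. The biopsy falls in the last 5 of these under protocol Appendix B. (SAP Appendix B gives 3 days for the same footnote, a separate mismatch to reconcile.)

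2. **What is scheduled in the interval.** Sections 7.2, 7.3.1 and 7.5.1 contain no AE recording. In Stage 1 the first AE entry comes after the infusion has started (7.3.4). In the Stage 2 text it first appears at Day 8 (7.5.4), although Appendix B marks AEs on Cycle 1 Day 1 without saying whether before or after dosing. Scheduled collection before Day 1 is nil; on Day 1 it is ambiguous.

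3. **What can still enter.** Under 8.1.1 the criteria for test or examination abnormalities and for laboratory or investigational abnormalities carry no time limit. Stable conditions are excluded only if present before the initial screening visit, so later findings can count. Section 8.2.1 also requires reporting of observed and spontaneously reported events, without a start date. Section 7.7 records AEs at unscheduled visits. Section 8.1.2 counts deaths as serious events from signed consent. Capture is therefore partial, not nil.

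4. **What the table would show.** Events under step 3 count only if the subject was later dosed, because the table uses the Safety Analysis Set. A death before the first dose is reportable but cannot appear in it. A Stage 2 subject who is enrolled, has a biopsy complication and is not dosed is replaced and leaves both numerator and denominator.

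5. **Whether the SAP wording closes the gap.** SAP 8.10 includes screening but covers only complications of a procedure that the protocol mandates. An optional biopsy may not qualify, so copying the SAP text into the protocol would leave the clearest example in doubt. The SAP also describes no pre-dose table.

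6. **Who can still benefit.** Section 3.3 plans about 23 subjects in Stage 2, and section 2.3.2 reports nine treated by 06 March 2017: 23 - 9 = about 14 remaining at that date. Section 2.3.2 also states that the Phase 1b portion is complete.

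**The case against.** The strongest reply is that this is a modest inconsistency between two documents. Starting routine AE collection at first dose is a common choice, the list in 8.1.1 is open, and several routes remain for pre-dose events. Section 8.6.2 further requires the investigator and the medical monitor to review unanticipated problems involving risk. The biopsy is optional, no uptake is stated, and the number of complications may be zero. The DLT and PFS endpoints are not affected.

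Much of this stands, and it rules out stronger readings that a reader might infer:

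- *That AEs are collected only once dosing starts, or that biopsy harms have no reporting route.* Step 3 of the check shows otherwise. What is missing is scheduled, uniform collection.
- *That the pre-dose table is empty by construction.* Untimed criteria, spontaneous reports and possibly the Day 1 assessment can fill part of it.
- *That all non-fatal biopsy complications are missed.* The documents support no such proportion.
- *That the biopsy is the only invasive procedure involved.* Section 6.1.3 allows infusion through an indwelling catheter, and a catheter used for the Day 1 infusion would be in place by then.

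What the reply does not answer is that the protocol itself chose to summarise the period from consent to first dose. Having done so, it needs a collection rule and a population that fit that summary, and it has neither.

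**Conclusion.** The concern holds as a mismatch between the planned summary, the collection rule and the analysis population, together with a conflict between protocol and SAP on the screening period. Non-fatal pre-dose harms, biopsy complications included, are not systematically collected over a nominal interval of up to 19 days. The planned table would be incomplete and selectively filled, and it would omit every enrolled subject who was never dosed.

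The number of events affected cannot be estimated, because the documents give neither biopsy uptake nor a complication rate. The conclusion assumes that sites follow the visit lists and Appendix B as written and that no eCRF instruction outside these documents sets an earlier start. The consequence is confined to safety reporting before the first dose.

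**What to change.** 1. State one AE start point in protocol 8.1.1 and 8.2.1, and align SAP 8.10 with it. At a minimum, collect procedure-related AEs and all serious AEs from signed consent.
2. Name the optional biopsy as a covered procedure.
3. Add AE recording to the screening list (7.2), to the pre-dose Day 1 list for Stage 2 (7.5.1) and to the screening column of Appendix B. Appendix A can be left, since Stage 1 is complete.
4. Put the pre-dose summary in the SAP on all enrolled subjects, so that those not dosed because of an event are counted. Section 5.2 defines enrolment by treatment assignment, so if a biopsy can be taken before assignment, consented subjects who had one should be included too. Otherwise delete the summary from 9.5.2.1.

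The cost is protocol and SAP wording and opening an existing form earlier; no visit or procedure is added. Sites will enter a few more events for the remaining Stage 2 subjects. Subjects already treated will lack the data, and the report should say so beside the table.

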8.1.2 Serious Adverse Events

A serious adverse event is defined as an untoward medical occurrence that results in any of the following outcomes:

- Death (i.e., all deaths occurring between signing of the consent form to within 30 days after last study drug administration), including deaths due to disease progression. Deaths that occur as a result of an adverse event that started during the study period should be reported. The reported adverse event should be the event that caused the death. Death is the outcome of this serious adverse event.
- Life-threatening situation (i.e., with an immediate risk of death from the event as it occurred but not including an event that, had it occurred in a more serious form, might have caused death).
- In-patient hospitalization or prolongation of existing hospitalization. Of note, an untoward medical occurrence that occurs during hospitalization is an adverse event but a complication that prolongs hospitalization is a serious adverse event. In-patient hospitalization comprises formal admission to a hospital for medical reasons, for any length of time, whether or not hospitalization extends overnight. However, hospital admissions for administration of the study drug, procedures required by the study protocol, or tumor-related diagnostic procedures are not considered serious.
- Persistent or significant disability/incapacity.
- Congenital anomaly/birth defect in the offspring of a subject who received the study drug.
- Other medically significant event. Such events may not be immediately life-threatening or result in death or hospitalization, but based upon appropriate medical and scientific judgment, may jeopardize the subject or may require medical or surgical intervention to prevent one of the outcomes listed above. Examples of such events might include:
 - Allergic bronchospasm requiring intensive treatment in an emergency room or at home
 - New cancers or blood dyscrasias
 - Convulsions that do not result in hospitalization
 - Development of drug dependency or drug abuse

8.2 Unexpected Adverse Event

An unexpected adverse event is defined as an event that has a nature or severity, or specificity that is not consistent with the applicable investigator brochure or that is symptomatically and pathophysiologically related to a known toxicity but differs because of greater severity or specificity. For example, under this definition, hepatic necrosis would be unexpected (by virtue of greater severity) if the investigator brochure only referred to elevated hepatic enzymes or hepatitis. Similarly, cerebral thromboembolism and cerebral vasculitis would be unexpected (by virtue of greater specificity) if the investigator brochure only listed cerebral vascular accidents.

“Unexpected,” as used in this definition, refers to an adverse drug experience that has not been previously observed and reported rather than an experience that has not been anticipated based on the pharmacological properties of the study drug.

8.2.1 Eliciting Adverse Event Information

The investigator is to report all directly observed adverse events and all adverse events spontaneously reported by the study subject. In addition, each study subject will be questioned about adverse events at each scheduled clinic visit or during each telephone contact with the subject following initiation of study drug administration. The type of question asked should be open-ended, e.g., *“Have you had any new health problems?”* or a similar type of query.

8.3 Reporting Procedures for All Adverse Events

All adverse events will be assessed by the investigator or qualified designee and recorded in the eCRFs. The investigator should attempt to establish a diagnosis of the event on the basis of signs, symptoms and/or other clinical information. In such cases, the diagnosis should be documented as the adverse event and/or serious adverse event and not described as the individual signs or symptoms. The following information should be recorded:

- Description of the adverse event using concise medical terminology
- Description as to whether or not the adverse event is serious (see Section 8.1.2)
- The start date (date of adverse event onset)
- The stop date (date of adverse event resolution)
- The severity of the adverse event (see Section 8.4)
- A description of the potential relatedness of the adverse event to study drug or a study procedure (see Section 8.5)
- The action taken due to the adverse event
- The outcome of the adverse event

